Electrocardiogram (ECG)		X			X	X	X	X	X	X	X	
Clinical laboratory tests ^h		X			X			X			X	
Blood sample for POPPK ⁱ		X			X			X			X	
Urine drug screen ^j		X			X			X			X	
Urine β-hCG ^k		X	X	X	X	X	X	X	X	X	X	X
Positive and Negative Syndrome Scale (PANSS)		X	X	X	X	X	X	X	X	X	X	

Table 2: Schedule of Assessments (Continued)

Study Visit Number Study Visit Week	Visit 1E ^a Baseline	Visit 2E Week 1	Visit 3E Week 2	Visit 4E Week 3	Visit 5E Week 4	Visit 6E Week 8	Visit 7E Week 12	Visit 8E Week 16	Visit 9E Week 20	Visit 10E Week 24	Visit 11E Week 26 or ET ^b	Visit 12E Week 27 Follow-up ^c EOS	
Study Visit Day	1	8 ± 2	15 ± 2	22 ± 2	29 ± 3	57 ± 3	85 ± 3	113 ± 3	141 ± 3	169 ± 3	183 ± 3	190 ± 2	
Brief Negative Symptoms Scale (BNSS)	↓	X	X	X	X	X	X	X	X	X	X		
Clinical Global Impression – Severity (CGI-S)		X	X	X	X	X	X	X	X	X	X	X	
Montgomery-Asberg Depression Rating Scale (MADRS)		X	X	X	X	X	X	X	X	X	X	X	
Columbia Suicide Severity Rating Scale (C-SSRS)		X	X	X	X	X	X	X	X	X	X	X	X
Drug effects questionnaire (DEQ)												X	X
Abnormal Involuntary Movement Scale (AIMS) ¹		X	X	X	X	X	X	X	X	X	X	X	
Barnes Akathisia Rating Scale (BARS) ¹		X	X	X	X	X	X	X	X	X	X	X	
Simpson-Angus Scale (SAS) ¹		X	X	X	X	X	X	X	X	X	X	X	
Pittsburg Sleep Quality Index (PSQI)		X				X		X			X	X	X
Cogstate Cognition Battery (CBB)													
Cogstate Schizophrenia Battery (CSB)								X				X	
USPA-B	X						X				X		

Abbreviations: AE = adverse event; AIMS = Abnormal Involuntary Movement Scale; BARS = Barnes Akathisia Rating Scale; β-hCG = human chorionic gonadotropin;

BNSS = Brief Negative Symptoms Scale; CGI-S = Clinical Global Impression – Severity; CBB = Cogstate Brief Battery; CSB = CogState Schizophrenia Battery;

C-SSRS = Columbia Suicide Severity Rating Scale ; ECG = Electrocardiogram; ET = early termination; MADRS = Asberg Depression Rating Scale; SAS = Simpson-Angus Scale; PANSS = Positive and Negative Syndrome Scale; PK = pharmacokinetic; PSQI = Pittsburg Sleep Quality Index;

^a Results of assessments from Visit 7 (Week 4) of Study SEP361-201 will serve as Baseline assessments for the present study. NOTE: Subjects may be hospitalized for the first week of the present study if deemed appropriate by the Investigator.

- ^b If a subject discontinues from the study, all Visit 11E procedures should be performed at the discontinuation visit, within 48 hours of last study dose.
- ^c All subjects will have a safety follow-up visit 7 (\pm 2) days after their last dose of study drug.

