- ^d All study drug will be taken once daily in the evening by mouth.
- ^e Telephone calls will be made by a member of the research staff to the subjects between scheduled study visits (between Weeks 1 and 2, and at Weeks 5, 7, 9, 11, 13, 15, 17, 19, 21, 23, and 25) to monitor clinical symptoms and adverse events. If subject appears to be symptomatic, an unscheduled visit will be made as early as possible.
- ^f Procedures and assessments for unscheduled visit are: drug accountability, physical and neurological examination, vital signs, ECG, clinical laboratory tests, urine drug screen, PANSS, CGI-S, MADRS, BNSS, AIMS, BARS, SAS, and C-SSRS.
- ^g Vital signs will include supine and standing measurements of blood pressure and heart rate and respiratory rate and temperature.
- ^h Clinical laboratory tests include: hematology, serum chemistry, urinalysis, serum prolactin, glycosylated hemoglobin (HbA_{1c}), and glucose and lipid panel (subjects must be fasted [no food or drink except water at least 8 hours] prior to collection of blood samples for glucose and lipid panel).
- ⁱ Blood samples for determination of plasma SEP-363856 and SEP-363854 concentrations will be collected at Visit 2E, 5E, 8E, and 11E (time and date of the 3 previous doses of study medication and the time of the blood sampling must be recorded). Time of food intake relative to study drug taken should be recorded.
- ^j Urine drug screen may be ordered at other visits as deemed clinically appropriate. These results should be discussed with the Medical Monitor.
- ^k Any positive urine β -hCG test should be confirmed by a serum β -hCG test.
- ^l Unscheduled BARS, AIMS, and SAS scales should be administered if a subject develops extrapyramidal symptoms (EPS) requiring treatment. See [Section 10.3](#).
- ^m Titration up to 75 mg/day is permitted (but not required) on Day 4 for reasons of efficacy as an unscheduled visit. At the minimum Investigator will assess AEs, concomitant medications and perform drug accountability at Day 4 unscheduled visit, all other assessments are not required but permitted based on Investigators judgment.

Note: With the exception of the DEQ and the USPA-B, all rating assessments will be performed by the rater using a tablet. In the event that a tablet is not available, the rating assessments will be performed by the rater using a paper version of the assessment.

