15.3.5. Efficacy Analyses

Efficacy data will be summarized descriptively for the safety population.

The absolute values of PANSS total score and subscale scores (positive, negative, and general psychopathology), CGI-S score, BNSS total score, and MADRS total score at both the DB baseline of study SEP361-201 and OL baseline of study SEP361-202, and at each scheduled post-baseline extension visit, will be summarized descriptively.

Changes from baseline in the above efficacy measures will be summarized at each scheduled post-baseline extension visit, based on both the DB baseline of study SEP361-201 and the OL baseline of study SEP361-202.

PANSS total score and CGI-S score data will also be separately summarized by age group, gender, race, and geographic region (i.e. US sites vs. non-US sites). Additional subgroup factors and details of the subgroup analysis will be provided in SAP.

The proportion of subjects who achieve a response, defined as a 20% or greater improvement (i.e. decrease) in PANSS total score from the baseline at the end of the 26-week open-label extension period, will be calculated based on: (1) the DB baseline of study SEP361-201 for subjects assigned to double-blind SEP-363856, and (2) the OL baseline of study SEP361-202 for subjects

assigned to double-blind placebo. For subjects who discontinue early, the PANSS total score measured at the early termination visit will be used.

The CBB composite score at the DB baseline of study SEP361-201 and OL baseline of study SEP361-202 will be calculated. The composite score based on the four domains contained in the CBB scale (i.e. attention, information processing, visual learning, and working memory) will be calculated from the CSB assessment result at Visit 7E (Week 12) and Visit 11E (Week 26) of study SEP361-202. The composite score of CSB at Visits 7E and 11E will also be calculated.

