15.3.6.8. Rate of Relapse and Time to Relapse

The relapse will be assessed in subjects who demonstrated clinical response to 4 weeks of treatment with SEP-363856. Clinical response is defined as meeting both of the following criteria:

- 1) a decrease in PANSS total score of $\geq 20\%$ from baseline, and
- 2) a CGI-S score ≤ 4 .

For subjects assigned to double-blind SEP-363856, clinical response will be evaluated using the Day 29 data of study SEP361-201, against the DB baseline of study SEP361-201. For subjects assigned to double-blind placebo, clinical response will be evaluated using the Day 29 data of study SEP361-202, against the OL baseline of study SEP361-202.

Relapse will be identified programmatically using the pre-defined criteria ([Section 6.2](#)) among subjects who demonstrated a clinical response to 4 weeks of treatment with SEP-363856. The rate of relapse will be calculated as the proportion of subjects with a relapse in the 26-week open-label extension period out of all subjects who demonstrated clinical response, along with the 95% confidence interval. The time-to-relapse will be summarized descriptively and will also be presented by a Kaplan-Meier plot.

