3.7. CHANGES TO ANALYSIS FROM PROTOCOL

- The protocol specified that for subjects *assigned* to double-blind SEP-363856, clinical response will be evaluated using the Day 29 data of study 361-201, against the DB baseline, and for subjects *assigned* to double-blind placebo, clinical response will be evaluated using the Day 29 data of study 361-202, against the OL baseline. Rather than the randomized treatment assigned to subjects, the analysis will be based on the *actual treatment received* during study 361-201. In addition, rather than using different baselines based on 361-201 treatment, DB baseline will be used for all subjects rolling over to 361-202, irrespective of the treatment they received in 361-201.
- The protocol specified that PANSS response rate will be calculated based on the DB baseline for subjects assigned to double-blind SEP-363856 and the OL baseline for subjects assigned to double-blind placebo. Rather than using different baselines based on 361-201 treatment, DB baseline will be used for all subjects rolling over to 361-202, irrespective of the treatment they received in 361-201.

Document: Documentation\SAP

Author:

Version Number:

Final V1.0

Version Date:

27FEB2019

Template No: CS_TP_BS016 Revision 4
 Effective Date: 01Apr2016

Reference: CS_WI_BS005

- The protocol specified that the total score will be used as a summary measure of the subject's ratings on the Simpson-Angus Rating Scale (SAS). Rather than the total score, the mean score will be used, which is calculated as the average of the 10 item scores.
- The protocol specified that one relapse criterion is emergence of suicidal ideation, homicidal ideation and/or risk of harm to self or others. The term 'suicidal ideation' is to be replaced by 'suicidality' and the term 'homicidal ideation' replaced by 'homicidality'. This is because the search criteria for AEs and C-SSRS data that meet this relapse criterion (see appendix 3) cover both suicidal ideation and suicidal behavior, and both homicidal ideation and homicidal behavior.

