6.3. DERIVED TIME POINTS

The last post OL baseline measurement collected in study 361-202 will be carried forward and will be defined as the last observation carried forward (LOCF) endpoint, using the post OL baseline value up to and including the Week 26 visit data.

The LOCF endpoint will be derived for the following endpoints: PANSS total score, PANSS subscale scores, PANSS five-factor model (Marder) factor scores, PANSS seven-factor model (UPSM) factor scores, CGI-S score, BNSS total score, MADRS total score, AIMS total score, AIMS global severity score (item 8), BARS total score, BARS individual item scores, SAS mean score, PSQI global score, CBB composite score and individual standardized scores of the 4 tests in CBB, UPSA-B total score, and the C-SSRS suicidal ideation score. In addition, the LOCF endpoint will be derived for the following data: vital signs, body weight, BMI, waist circumference, ECG, clinical laboratories, and urine drug screen.

Both scheduled and unscheduled assessments as well as the early termination assessments that are collected post OL baseline will contribute to the derivation of the LOCF endpoint.

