16.2.6. RATE OF RELAPSE AND TIME TO RELAPSE

Subjects demonstrating a relapse of psychotic symptoms during the OL extension treatment period will be identified on the relapse population.

Relapse is defined as the earliest occurrence of any of the following:

- An increase in PANSS total score by $\geq 30\%$ from the PANSS total score at clinical response and a CGI-S score ≥ 3

Document: Documentation\SAP

Author:

Version Number:

Final V1.0

Version Date:

27FEB2019

Template No: CS_TP_BS016 Revision 4
 Effective Date: 01Apr2016

Reference: CS_WI_BS005

Copyright © 2009, 2010, 2012, 2016 Quintiles Transnational Corp. All rights reserved.

The contents of this document are confidential and proprietary to Quintiles Transnational Corp. Unauthorized use, disclosure or reproduction is strictly prohibited.

- Re-hospitalization for worsening of psychosis
- Emergence of suicidality, homicidality, and/or risk of harm to self or others

PANSS and CGI-S assessments taken at both scheduled and unscheduled visits will be considered when identifying the relapse event. Occurrence of re-hospitalization for worsening of psychosis will be identified by medical review of the data collected on the Psychiatric Hospitalization CRF page as well as the SAEs prior to database lock. Emergence of suicidality, homicidality, and/or risk of harm to self or others will be identified as outlined in Appendix 3. The evaluation period for relapse will be from the day/time of clinical response to 1 day after the day of the last dose of extension study medication.

The date of relapse is defined as the earliest of: the date of the assessment (based on the QSSTDTC variable in Bracket data) at which the qualifying PANSS and CGI-S data were collected, the date of hospital admission for worsening of psychosis, the date of the assessment (based on the QSSTDTC variable in Bracket data) at which a qualifying C-SSRS event is identified, or the start date of the qualifying adverse event.

The date of clinical response is defined as the date of the PANSS and CGI-S assessments (based on the QSSTDTC variable in Bracket data) which established clinical response.

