Time-to-relapse (in days) is defined as the date of relapse – the date of clinical response + 1. Subjects completing/discontinuing from the study without meeting the criteria for relapse will be censored on the day after the last dose of extension study medication. Kaplan-Meier estimates of the median time-to-relapse and the 25th percentile and 75th percentile of time-to-relapse, along with the respective 95% confidence intervals, will be calculated. Kaplan-Meier estimate of the probability of relapse at the end of the OL extension treatment period, and its 95% confidence interval, will also be calculated. The time-to-relapse data will be presented in a Kaplan-Meier curve.

The rate of relapse will be calculated as the proportion of subjects demonstrating a relapse during the OL extension treatment period in the relapse population. The 95% confidence interval for the rate of relapse will also be calculated.

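### Relapse evaluation and censoring stop one calendar day after the last dose, but a compliant early-termination visit can fall on the second day, so a relapse first found there is counted as relapse-free

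*SAP*

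**What the plan says.** Let D be the calendar day of the last dose of extension medication.

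- **Relapse window.** SAP 16.2.6: the "evaluation period for relapse will be from the day/time of clinical response to 1 day after the day of the last dose" (that is, D+1). Subjects who finish or leave without a relapse "will be censored on the day after the last dose of extension study medication". A relapse found on PANSS/CGI-S or on the C-SSRS is dated to the assessment itself.
- **Visit window.** Footnote b of the schedule (Protocol Table 2, repeated in SAP Table 1): "all Visit 11E procedures should be performed at the discontinuation visit, within 48 hours of last study dose". Protocol 11.6.9 lists PANSS, CGI-S and C-SSRS among the Visit 11E/ET procedures.
- **Dose timing.** Footnote d of the same table: "All study drug will be taken once daily in the evening by mouth".
- **ET data in other analyses.** SAP 6.3 says that "early termination assessments that are collected post OL baseline will contribute to the derivation of the LOCF endpoint", with no limit tied to the last dose. For PANSS response, Protocol 15.3.5 says: "For subjects who discontinue early, the PANSS total score measured at the early termination visit will be used".
- **Protocol definition of the rate.** Protocol 15.3.6.8 takes the "proportion of subjects with a relapse in the 26-week open-label extension period out of all subjects who demonstrated clinical response", again with no last-dose limit.

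**The concern.** The relapse window is set in calendar days and the ET window in hours, and the two do not match. Forty-eight hours after any evening dose ends on D+2, so the plan permits a visit that its own relapse rule then ignores.

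The subjects exposed to this are early terminators. The protocol lets subjects leave for lack of efficacy (13.1). It also has them discontinued if they need another antipsychotic (10.3.3) or report C-SSRS Type 4 or 5 ideation (11.4.7.4). Relapse is most plausible in this group, and the ET visit may be where it is first documented. The C-SSRS version in use looks back to the previous visit, so a D+2 assessment can report behaviour that occurred on drug and still be dated outside the window.

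Relapse rate and time to relapse are the stated measures for the secondary objective on maintenance of response. Dropping an event and censoring the subject a day earlier cannot raise either the rate or the Kaplan-Meier relapse probability.

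**Working it through.** The plan states no figure to reproduce. The check is calendar arithmetic, then a reading for any text that would bring the visit back, then the scale.

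**1. Hours covered.** Inputs: window closes at the end of D+1 (SAP 16.2.6); ET visit allowed to 48 hours (footnote b); evening dosing (footnote d). No clock time is given, so 18:00 to 23:00 is assumed.

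Hours covered = (24 − dose hour) + 24. Hours uncovered = 48 − hours covered.

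| Dose time on D | Covered | Uncovered | Uncovered share |
|---|---|---|---|
| 18:00 | 6 + 24 = 30 h | 18 h | 18/48 = 37.5% |
| 21:00 | 3 + 24 = 27 h | 21 h | 21/48 = 43.8% |
| 23:00 | 1 + 24 = 25 h | 23 h | 23/48 = 47.9% |

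**2. Visits in clinic hours on D+2** (08:00 to 17:00 assumed).
- Shortest gap, 23:00 dose to 08:00: 1 + 24 + 8 = 33 h.
- Longest gap, 18:00 dose to 17:00: 6 + 24 + 17 = 47 h.

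Every such visit is within 48 hours, and none is inside the relapse window.

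**3. Does anything bring the visit back?**
- SAP 6.4 assigns ET data to the next planned visit. That changes the visit label, not the assessment date on which SAP 16.2.6 relies.
- SAP 16.2.6 accepts scheduled and unscheduled PANSS/CGI-S, but only within its evaluation period.
- SAP 3.7 lists changes from the protocol down to the wording of one relapse criterion ("The protocol specified that one relapse criterion is emergence of suicidal ideation, homicidal ideation and/or risk of harm to self or others"), but not this cut-off.

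**4. A worked subject** (invented scores).
- Double-blind baseline PANSS 100; Week 4 PANSS 80 with CGI-S 4. Change: −20/100 = −20.0% raw, or −20/(100 − 30) = −28.6% by SAP 6.7. A clinical response on either scale.
- ET on D+2: PANSS 104, CGI-S 5. Rise from response: 24/80 = 30.0% raw, or 24/(80 − 30) = 48.0% with 30 subtracted. The relapse criterion is met on either scale.
- PANSS response at LOCF (SAP 16.1.5): (104 − 100)/(100 − 30) = +5.7%, a non-responder.
- Relapse analysis (SAP 16.2.6): censored on D+1, relapse-free.

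**5. Scale per lost relapse.** Each one moves the rate by 1/n, where n is the relapse population, which the documents do not state. It is a subset of entrants, anticipated at about 180 (Protocol 15.1; SAP 3.3).
- n = 180, the upper limit: 1/180 = 0.56 points.
- n = 90, half of entrants as responders (assumption): 1/90 = 1.11 points.

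As an illustration with n = 90, 9 counted relapses give 10.0% (Clopper-Pearson 95% CI 4.7 to 18.1). Recovering 3 more gives 12/90 = 13.3% (7.1 to 22.1). Both counts are assumed.

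**The case against.** The strongest reply is that the affected case is narrow. With evening dosing, a subject still taking drug who is assessed and discontinued at a visit took the last dose the evening before, so that visit is D+1 and counts. This covers relapse found at a scheduled visit, at an unscheduled visit for symptoms, or through a C-SSRS finding that itself triggers discontinuation. A loss needs a responder who did not take the previous evening's dose, whose ET visit falls on D+2, and who has no qualifying assessment, admission or adverse event dated by D+1. This is correct, and the documents do not show how often it happens. The uncovered share in the table is likewise a share of clock hours, not of visits or relapses.

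Second, an on-treatment window is a legitimate choice, and D+1 could be read as the treatment period plus one day. That explains having a cut-off but not this one. Protocol Table 7 places Visit 11E inside the open-label treatment period, and the SAP gives no reason for closing the window before that visit's own tolerance ends. By contrast, the 9-day limit for adverse events in SAP 17.1 matches the follow-up visit at 7 ± 2 days.

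Third, response and relapse use different references and thresholds, so being an LOCF non-responder and relapse-free is not contradictory in itself. An ET PANSS of 90 in the worked subject gives −10/70 = −14.3% at LOCF and +10/80 = +12.5% from response: a non-responder with no PANSS relapse under any window. That stands. What the example does show is that one assessment meeting the relapse criterion is used in one analysis and discarded in the other.

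Fourth, a D+2 bound also admits hospital admissions and adverse events dated D+2. It does, but an admission counts only if medical review finds worsening of psychosis, and the extension is one calendar day.

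**Conclusion.** The concern holds. Followed as written, SAP 16.2.6 turns a qualifying relapse at a compliant D+2 visit into a relapse-free censoring on D+1. This is true for any evening dose time; the assumed clock times affect only how many hours are uncovered.

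The reach is limited. ET visits on D or D+1, and relapses with an admission, qualifying adverse event or earlier assessment dated by D+1, are counted correctly. The 48-hour rule applies to discontinuation visits, so the gap concerns early terminators. The number of relapses lost cannot be derived; each costs at least 0.56 points if about 180 enter, and 1.1 points if half of those are responders. The primary endpoint is unaffected and no hypothesis is tested. The point should still be fixed, because the loss runs in one direction on a reported secondary measure.

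**What to change.** In SAP 16.2.6, end the evaluation period 2 days after the day of the last dose, so that it takes in the ET/Visit 11E assessment made within the 48-hour window. Use the same bound for censoring. Add a bullet to SAP 3.7 recording the cut-off, because the protocol definition has none. If the SAP is not reissued, SAP 20 provides for describing and justifying the change in the final report.

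The cost is two phrases in 16.2.6, one bullet in 3.7 and one date bound in the program, with no new data. The downside is up to one more off-drug day in the evaluation period, which can bring in an admission or adverse event dated D+2, and possibly a slightly higher reported relapse rate.

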10.3.3. Prohibited Medications

All antipsychotics (except for study drug treatment), antidepressants and mood stabilizers (eg, lithium, divalproex/valproic acid, carbamazepine, lamotrigine, etc.) are not permitted during the study.

Subjects who require treatment with one or more of prohibited concomitant medications (including antipsychotics [other than study drug treatment] or anxiolytics [lorazepam or equivalent above protocol-specified limits]) will be discontinued (as appropriate) from the study. Limited use of these medications immediately prior to study discontinuation is permitted and will not constitute a protocol deviation.

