13. TERMINATION OF SUBJECT FROM STUDY/DISCONTINUATION OF STUDY DRUG

13.1. Criteria for Subject Termination/Study Drug Discontinuation

Subjects may be discontinued from the study drug at any time for any of the following reasons:

- Adverse event (specify)
- Lack of efficacy (specify)
- Withdrawal by subject (specify)
- Non-compliance with study drug (specify)
- Protocol deviation (specify)
- Death
- Progressive disease
- Pregnancy
- Other (specify)

If at any time during the course of the study, in the opinion of the Investigator, the subject may no longer safely participate due to a change in medical status (eg, experiences an AE, becomes pregnant), the subject must be discontinued from the study drug. Subjects discontinued from study drug will be discontinued from the study.

The reason and information on the epoch for study drug discontinuation will be recorded on the appropriate CRF. In case of death, the date of death should be captured on the CRF.

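### Responders who leave because they are worsening, but meet none of the three relapse criteria inside the window, are non-events in the crude rate and censored in the Kaplan-Meier analysis, which plausibly understates loss of response

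*SAP*

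**What the plan says.** SAP 16.2.6 defines relapse, within the relapse population of four-week responders (SAP 5.2), as the earliest of three events:

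- a PANSS total rise of at least 30% "from the PANSS total score at clinical response and a CGI-S score" of at least 3;
- "Re-hospitalization for worsening of psychosis";
- "Emergence of suicidality, homicidality, and/or risk of harm to self or others", identified through Appendix 3.

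The evaluation period ends one day after the day of the last extension dose. On censoring the SAP states: "Subjects completing/discontinuing from the study without meeting the criteria for relapse will be censored on the day after the last dose of extension study medication". On the crude rate: "The rate of relapse will be calculated as the proportion of subjects demonstrating a relapse during the OL extension treatment period in the relapse population".

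Some exits caused by failing response are expected under the protocol. Section 10.3.3 provides for discontinuation, as appropriate, of "Subjects who require treatment with one or more of prohibited concomitant medications (including antipsychotics [other than study drug treatment", and section 13.1 lists "Lack of efficacy (specify" and progressive disease among the reasons for stopping. Section 13.1 adds: "Subjects discontinued from study drug will be discontinued from the study". None of these exits is itself a relapse criterion. No supportive or sensitivity analysis is planned for relapse: Protocol 15.3.11 plans none, and SAP 16.2.6 adds none.

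**The concern.** Rate of relapse and time to relapse are the only stated measures of long-term maintenance of response (Protocol 5.2, SAP 2.2). The protocol removes subjects who are failing, while the SAP counts only those who also cross one of three thresholds before the window closes. A responder who deteriorates and is withdrawn short of a threshold stays in the crude denominator as a non-relapse. In the Kaplan-Meier analysis the same subject is censored, which is valid only if leavers and stayers share the same later risk. That is doubtful when worsening is the reason for leaving.

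With a single arm, the absolute figure is the result; no control group carries the same bias. If enough responders leave this way, the study reports better maintenance of response than it observed, and the gap grows the sooner sites withdraw worsening subjects.

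**Working it through.** The plan states no relapse rate, dropout rate, responder count or power for this endpoint, so there is no figure to reproduce. The 180 in SAP 3.3 is an anticipated rollover number.

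**Step 1. Does the PANSS criterion catch a subject who has lost the whole response?** Inputs: response is a fall of at least 20% from double-blind baseline B (SAP 5.2); percent change uses a denominator of B - 30 (SAP 6.7); relapse is a rise of at least 30% from the response score S (SAP 16.2.6). SAP 6.7 is worded for change from baseline, so the formula for the 30% rise is not settled. Both readings are shown.

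For exactly 20% improvement:

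- S = B - 0.20 × (B - 30) = 0.80B + 6
- Raw reading: threshold = 1.30 × S = 1.04B + 7.8
- Minus-30 reading: threshold = 30 + 1.30 × (S - 30) = 30 + 1.04 × (B - 30)

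Both exceed B for any B above 30. With an assumed B of 100, S = 86 and relapse needs 1.30 × 86 = 111.8 (raw) or 30 + 1.30 × 56 = 102.8 (minus-30). Full return to 100 does not qualify on either reading.

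Return to B qualifies only if the initial improvement was at least 1 - 1/1.30 = 23.1% on the minus-30 reading. On the raw reading it must be at least (B - B/1.30)/(B - 30), which is 36.9%, 33.0% and 30.8% for B of 80, 100 and 120.

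**Step 2. Does the exit visit fall inside the window?** The window closes one day after the day of the last dose (SAP 16.2.6). Early-termination procedures, including PANSS and CGI-S, may take place up to 48 hours after the last dose (footnote b to the schedule of assessments; Protocol 11.6.9). Dosing is in the evening (Protocol 10.1). A visit on the second morning after the last dose is within 48 hours but two calendar days later. A qualifying PANSS and CGI-S at that visit is therefore excluded.

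**Step 3. Crude rate, assumed counts.** Take 90 responders and 9 relapses by the three criteria: 9/90 = 10.0% (exact 95% CI 4.7-18.1). Adding exits for failing response that meet no criterion:

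| Such exits | Events | Rate (exact 95% CI) |
|---|---|---|
| 4 | 13/90 | 14.4% (7.9-23.4) |
| 9 | 18/90 | 20.0% (12.3-29.8) |
| 18 | 27/90 | 30.0% (20.8-40.6) |

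The shortfall is the share of responders leaving this way. Over 60-120 responders, about 10-15% relapsing and about 5-20% such exits, the rate moves from 10.0-15.6% to 14.4-35.6%.

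**Step 4. Kaplan-Meier, assumed constant hazards.** Let r = 10% relapse, o = 15% leave for other reasons, and q leave for failing response. With T = r + q + o and H = -ln(1 - T), the expected risk is 1 - exp(-H × r/T) if these exits are censored and 1 - exp(-H × (r + q)/T) if they are events. For q = 10%: T = 0.35 and H = 0.431, giving 1 - exp(-0.123) = 11.6% and 1 - exp(-0.246) = 21.8%. For q = 5% the pair is 11.2% and 16.3%; for q = 20% it is 12.4% and 32.9%.

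**The case against.** A reader might infer that every responder withdrawn for worsening is scored as a non-relapse. The documents do not support that. The early-termination visit includes PANSS and CGI-S, and Protocol 13.2 asks for every effort to complete it. A symptomatic telephone contact triggers an unscheduled visit with PANSS, CGI-S and C-SSRS (Protocol 11.6.11), and unscheduled data feed relapse identification (SAP 6.4, 16.2.6). Psychiatric admissions are found by medical review, and Appendix 3 is broad, including aggression, anger and hostility. Many worsening leavers will be counted. What stands is the group missed by every route, and Steps 1 and 2 show that it need not be empty.

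A reader might also take a response score of 80 followed by withdrawal at 100 as a clear miss. It is one only on the raw reading (threshold 104). On the minus-30 reading the threshold is 80 + 0.30 × 50 = 95, and that subject is a relapse if CGI-S is at least 3. The example in Step 1 holds either way.

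Nor does Protocol 15.3.11 close the door on supportive analyses. The SAP adds one for BNSS (16.2.3) and analyses cognition with and without integrity failures (16.2.4). It simply plans none for relapse.

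The remaining objections have weight. The crude rate measures relapse as the protocol defines it; a measure that includes exits for failing response is wider, not the true value of the same quantity. The Kaplan-Meier direction needs a higher later hazard among leavers, which is plausible but not shown. Disposition reasons, AEs leading to discontinuation and the LOCF response rate expose some of this deterioration, though for the safety population rather than the relapse population. Relapse is an exploratory secondary measure in a study without hypothesis tests (Protocol 4.4, 5.2).

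**Conclusion.** The point holds for responders who leave because of lack of efficacy, psychotic worsening or need for another antipsychotic and who meet no relapse criterion inside the window. Their handling plausibly understates loss of response. The PANSS criterion is not a dependable safeguard, and the one-day window can exclude a qualifying exit assessment.

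The size cannot be computed from the documents. In the crude rate, the shortfall against a loss-of-response measure equals the share of responders leaving this way: 5-20 points if that share is 5-20%, which is an assumption. It would be tempting to conclude that the reported rate will be half the real one or less. That follows only if such exits are assumed to be at least as many as the criterion relapses and all are treated as relapse; the documents support neither assumption. This is a worthwhile, inexpensive improvement to a secondary estimate and leaves the primary safety objective untouched.

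**What to change.** Keep the current definition as the main analysis. In SAP 16.2.6:

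1. Add one prespecified supportive analysis (crude rate and Kaplan-Meier) that also counts as events discontinuations for lack of efficacy, progressive disease or an AE of psychotic worsening. Count the start of another antipsychotic only when its recorded indication is psychotic worsening. Counting every such start would misclassify a responder who leaves for an unrelated reason and is given a replacement, since Protocol 10.3.3 permits limited use just before exit. Identify these events by medical review before database lock, as is already done for re-hospitalization, and state how they are dated.
2. Extend the analysis window for PANSS and CGI-S so that it includes the early-termination visit.
3. Tabulate censored subjects in the relapse population by reason for discontinuation.

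Discontinuation reason, AE terms, and medication start date and indication are already collected (Protocol 13.1, 12.3, 10.3). No visit, treatment or withdrawal rule changes. The cost is some extra medical review, one repeated table and curve, and one small table. The second figure may be less favourable, and it may count some leavers who had not truly lost response, which is why it should support the main estimate and not replace it.
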